
**Aim 1:** To characterize the acute effects of PO psilocybin 25 mg/70 kg, 30 mg/70 kg, and 40 mg/70 kg in alcohol dependent patients: Hypothesis 1: The drug will be well-tolerated, and acute effects will be similar to those observed in normal volunteers.

**Aim 2:** To evaluate the effect of psilocybin treatment on drinking outcomes for 32 weeks after the first administration, relative to diphenhydramine control. Hypothesis 2: A greater decrease in percent heavy drinking days will be observed among participants receiving psychoactive doses of psilocybin in combination with psychosocial treatment than in those receiving diphenhydramine.

**Aim 3:** To test whether or not characteristics of the drug administration session experiences mediate effects of psilocybin on short term (1 week) persisting effects and post-session drinking behavior. Hypothesis 3: Intensity of experience during the drug administration sessions will predict post-session changes in craving, self-efficacy, and motivation, and these changes will in turn predict changes in drinking behavior during the 32 weeks following initial drug administration.

**Aim 4:** To evaluate the explanatory value of changes in alcohol craving, self-efficacy, motivation, and other psychological domains in accounting for the observed experimental effect of psilocybin relative to diphenhydramine control. Hypothesis 4: Changes in craving, self-efficacy, and motivation will mediate the effects of psilocybin treatment on drinking behavior.

**Aim 5:** To evaluate pre-post changes in drinking in participants after they receive psilocybin in the third session. Hypothesis 5: participants in the control group will show decreases in drinking during the 16 weeks following the psilocybin session at week 38.

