### 3.3.5 Randomization and Blinding

Randomization will be performed as close as possible to the first drug administration session (on the morning of the session if possible) in order to restrict the intent-to-treat sample to patients who actually receive study medication. The randomization will be stratified by site and will consist of balanced varied size blocks within strata to ensure relative equality of assignment across treatment groups. The block sizes will not be revealed to participating investigators and will be randomly selected from a small number of different block sizes to help reduce the likelihood of an investigator predicting the next treatment assignment. The study statistician will generate the randomization scheme for each site, and the study pharmacist will assign treatment sequentially according the sequence for each site.

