### **3.3.7 Sites**

Up to 4 sites will participate in the trial. Sites will be selected on the basis of experience with administration of classic hallucinogens, other clinical trial experience, available staff, available facilities, regulatory approvals, and institutional support.

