### **3.3.12 Statistical analysis and power**

A full description of the planned analyses for this trial can be found in the Statistical Analysis Plan (SAP)

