### 3.3.12.3.2 Method

For PHDD we will employ a MMRM including fixed, categorical effects of treatment, assessment, and site; site-by-treatment and treatment-by-assessment interactions; the continuous, a fixed covariate (week 1-4 PHDD); and using monthly values of PHDD (weeks 5-8, 9-12, 13-16, 17-20, 21-24, 25-28, 29-32, 32-36) as the dependent measure. Site and the site-by-treatment interaction will be removed from the final model if not significant at the  $p < 0.05$  level. Secondary drinking measures with a continuous scale of measurement, i.e., PDA and DPDD, will be tested in a similar fashion and for days to first drinking day and days to first heavy drinking day (5 or more standard drinks for a man, 4 or more standard drinks for a woman). Cox survival analysis will be used. Measures of effect size will be calculated for all planned between-group contrasts (Hedges  $d$ ) and the  $Q$  statistic will be calculated to assess the homogeneity of effect across the primary and secondary outcome measures of drinking.

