#### **3.3.12.7 Statistical power**

Power analysis is based on the primary outcome analysis contrasting the psilocybin group with the control group with respect to percent heavy drinking days in months 1-8 post pharmacologic treatment (Aim 2). With a total sample size of  $n = 180$  (90 assigned to psilocybin and 90 to control), and 5% attrition (realistic because useable data require only 1 month follow-up in participants who have already participated for 1 month,  $N = 171$ ) our power analysis was based on the assumption that four predictors would be in the regression-based HLM model. We estimate that the study has power of 0.8 to detect an effect of size  $f^2 = .065$ , with alpha = 0.05 (2-tailed) and no correction for multiple comparisons. This effect is comparable to that of naltrexone [9, 158, 159], and smaller than those observed in some recent trials of other promising medications [160-162]. Regardless of the statistical significance of these changes, standardized and non-standardized effect sizes will be computed for primary and secondary outcome variables. The addition of an open-label optional third dosing does not affect the required sample size for Aim 2 (primary outcome), but approximately doubles the sample size for Aim 1 and allows for the addition of Aim 5.

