#### **3.3.13 Study Milestones**

We propose to implement the study in three stages, with interim analyses and DSMB review after the first and second stages.

Stage 1: Following final protocol approval by all necessary authorities and procurement of necessary funding, staff will be trained, at least 4 pilot/training participants per site will be treated, and 20 participants will be randomized into the main trial across two sites (UNM and NYU, 10 per site). At the end of this stage, feasibility and tolerability will be assessed, and necessary protocol modifications may be made.

Stage 2: An additional 80 participants will be randomized, with the possible addition of one or two additional sites to enhance recruitment capacity. At the end of this stage, interim checks of attrition rates and the assumed error standard deviation  $\sigma$  for the primary outcome measure will be conducted to assess the adequacy of the projected study sample size. This check will be performed by an unblinded statistician, who will estimate the primary model, and report back on error variance and drop-out rates. Additional necessary protocol modifications may be made, and final sample size will be determined. In addition, safety interim looks will be performed (without formal statistical testing) at the regular DSMB meetings or unscheduled times per the DSMB's request. Although at this time we are not planning a formal statistical interim analysis for efficacy or futility, such an interim analysis can be performed if requested by the DSMB or the sponsor.

Stage 3: Assuming 180 participants are required, the 80 remaining participants will be randomized, with an additional 9 months to complete treatment and assessment of the final participants.

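### A p < 0.05 test on the outcome decides whether site terms stay in the primary PHDD model, and the averaging across sites is not stated if the interaction stays (minor)

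*Combined protocol and SAP*

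**What the plan says.** Section 3.3.12.3.2 analyses eight four-weekly PHDD values with an MMRM. Its terms are treatment, assessment, site, the interactions of treatment with site and with assessment, and PHDD in weeks 1-4 as a covariate. It then adds: "Site and the site-by-treatment interaction will be removed from the final model if not significant" at p < 0.05. It does not say whether the two site terms are tested jointly or in sequence. The rule extends to the continuous secondary outcomes: "PDA and DPDD, will be tested in a similar fashion".

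Section 3.3.5 states: "The randomization will be stratified by site". On the number of sites, section 3.3.7 says "Up to 4 sites will participate in the trial", and section 3.3.13 describes stage 2 "with the possible addition of one or two additional sites to enhance recruitment capacity".

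Hypothesis 2 in section 2 reads in part: "A greater decrease in percent heavy drinking days will be observed among participants receiving psychoactive doses of psilocybin". Section 3.3.12.3.1 fixes the window at weeks 5-36. Section 3.3.12 refers to a separate SAP for full detail; no SAP text on this point was available.

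**The concern.** Two things are left to the data or left unsaid.

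- **Choice of model.** A test on the outcome settles which primary model is fitted, and it can remove the factor used to stratify randomisation. The protocol does not do this everywhere: for Aim 4 (section 3.3.12.5.2) it leaves site terms out in advance, without a test.
- **Averaging over sites.** Once site-by-treatment is in the model, there is no single treatment effect until weights are chosen for the sites. Weighting by site size and weighting sites equally are both ordinary choices, and they target different quantities when sites differ in size and in effect. Hypothesis 2 speaks of participants overall, which fits size weighting, but the method section does not say so.

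At stake are the error rate of the primary test and, if sites truly differ, what that test is about.

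**Working it through.** **Inputs from the protocol.** Section 3.3.12.7 gives 180 randomised 1:1 and 5% attrition, so 180 × 0.95 = 171 analysable; two-sided alpha 0.05; f² = 0.065; power 0.80; four predictors. There are two to four sites. Neither final site sizes nor between-site differences are given.

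**The plan's own figure.** For "We estimate that the study has power of 0.8", the noncentrality is λ = f² × N = 0.065 × 171 = 11.1. The noncentral F distribution gives power 0.798 with 3 tested degrees of freedom, 0.754 with 4 and 0.912 with 1. The stated 0.80 is thus reproduced only with 3 tested df, which the section does not specify. A treatment term has 1 df. For it, 80% power at N = 171 needs f² = 0.0464, so d = 2√0.0464 = 0.43; the stated f² corresponds to d = 2√0.065 = 0.51. I use d = 0.43 so that comparisons start from 80%.

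**Assumptions.** ANCOVA analogue of the MMRM effect averaged over the eight months; complete data; 1:1 within site; residual SD 1; between-site SD 0.3; N = 171. The interaction is tested at 0.05; if it is dropped, site is tested at 0.05. Site sizes and site-specific effects are assumed. A full MMRM was not simulated.

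**Why weights matter.** With 1:1 allocation, a site of size n has effect variance 4/n.

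- Size weights: SE = 2/√171 = 0.153.
- Equal weights, two sites: SE = √(1/n₁ + 1/n₂). At 86/85 this is 0.153; at 130/41 it is √(1/130 + 1/41) = 0.179.

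**No true effect** (1,000,000 runs per layout). Always keeping site gives 5.0%. The rule with size weights gives 5.0% in all eight layouts. The rule with equal weights gives:

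| Site sizes | Type I error |
|---|---|
| 86/85; 57/57/57; 43/43/43/42 | 5.0% each |
| 120/51 | 5.5% |
| 130/41 | 5.8% |
| 100/50/21 | 5.6% |
| 90/50/20/11 | 5.7% |
| 90/60/11/10 | 5.8% |

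A repeat with whole-number arms gives 5.4-5.8% for the unequal layouts.

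The mechanism shows in a separate, more lopsided run at 137/34 (20,000 runs). The interaction is kept in 4.94% of null trials. Within those, the equal-weight test rejects 25.5% and the size-weight test 6.2%. The contributions are 0.0494 × 0.255 = 1.26 points and 0.0494 × 0.062 = 0.31 points. The gap of 0.95 points is the difference between 6.00% and 5.05% overall.

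Pre-testing site alone gives 4.9-5.0%. Never including site gives 4.3-4.7%, with a 2-3% larger SE.

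A check with bounded 28-day counts, the baseline covariate and 10% dropout (20,000 runs, Monte Carlo SE 0.16 points) gives 5.1-5.2% with site kept or size weights. Equal weights give 5.1% (86/85), 6.2% (130/41) and 6.1% (90/50/20/11).

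**Uniform effect, d = 0.43** (400,000 runs). Always keeping site gives 79.9-80.0%, and the rule with size weights 80%. The rule with equal weights gives 78.4-79.3% across the five unequal layouts.

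**Truly different site effects** (200,000 runs), power in %:

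| Sizes | Effects (SD) | Site always kept | Rule, size weights | Rule, equal weights | Equal minus size |
|---|---|---|---|---|---|
| 130/41 | 0.5, 0 | 69.3 | 69.6 | 52.5 | −17.1 |
| 130/41 | 0.2, 0.8 | 60.3 | 60.8 | 73.1 | +12.3 |
| 120/51 | 0.5, 0 | 62.1 | 62.6 | 47.9 | −14.7 |
| 120/51 | 0.2, 0.8 | 68.7 | 69.3 | 79.2 | +9.9 |
| 100/50/21 | 0.5, 0.5, 0 | 81.3 | 81.4 | 72.3 | −9.1 |
| 100/50/21 | 0.2, 0.2, 0.8 | 42.4 | 42.6 | 49.9 | +7.3 |
| 90/50/20/11 | 0.5, 0.5, 0, 0 | 75.5 | 75.7 | 65.0 | −10.7 |
| 90/50/20/11 | 0.2, 0.2, 0.8, 0.8 | 51.1 | 51.4 | 58.9 | +7.5 |
| 86/85 | 0.5, 0 | 36.6 | 37.1 | 36.9 | −0.2 |
| 86/85 | 0.2, 0.8 | 89.5 | 89.8 | 90.0 | +0.2 |

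At 130/41 the interaction is kept in 28% of trials (0.5/0) and 38% (0.2/0.8). The target itself moves. With 0.5/0, size weights give (130 × 0.5 + 41 × 0)/171 = 0.38 SD and equal weights 0.25 SD. With 0.2/0.8, they give (130 × 0.2 + 41 × 0.8)/171 = 0.34 SD and 0.50 SD.

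**The case against.** The case for leaving the text alone is substantial. The deletion rule is written down in advance, so there is no discretion over which terms go. With no true interaction, the term stays in only about 5% of trials. Size weighting, the reading closest to Hypothesis 2, makes the rule harmless. The cited SAP may already fix the weighting. The only site sizes in the protocol are equal (10 at each of two sites in stage 1, section 3.3.13). All of this stands, and it is why the point is minor. What remains is that the method section does not state the averaging, and that keeping the stratification factor throughout costs almost nothing.

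A reader might infer more than the documents support:

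- **That the primary comparison is undefined.** It is not. The drugs, outcome and window are named; only the averaging over sites is open, and only if the interaction stays.
- **That testing site terms on the outcome materially inflates type I error.** With size weights or near-equal sites it does not, and leaving site out makes the test slightly conservative.
- **That error could reach 5.7-7.5%, or about 8%.** The first range needs one reference site's coefficient to be read as the treatment effect; the second needs the most favourable contrast to be picked after seeing the data. Section 3.3.12.3.2 suggests neither.
- **That a 17-point power swing is a defect of the plan as such.** It needs assumed lopsided sites and assumed strong heterogeneity, and it compares tests of different target effects.

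**Conclusion.** The point holds as a minor one. The rule makes the primary model depend on outcome tests, and the available text leaves the averaging over sites unstated if the interaction is retained. The pre-test itself costs almost nothing. Under equal weights and unequal sites, type I error rises by under one percentage point in the main simulations (just over one in the bounded-outcome check at 130/41), and power under a uniform effect falls by at most 1.6 points. Larger consequences need unequal sites, truly different effects and equal weights together.

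Unequal sites are possible, since one or two may join after stage 1, but nothing shows that they will occur. The figures rest on assumed site sizes, sequential testing, an ANCOVA analogue and d = 0.43 rather than the effect implied by the stated f². If the SAP already fixes the weighting, alignment of the two texts is all that the weighting issue needs.

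**What to change.** In section 3.3.12.3.2, specify one primary MMRM with treatment, assessment, treatment-by-assessment, week 1-4 PHDD and site always retained, and delete the p < 0.05 removal rule. Report site-by-treatment separately as a supportive heterogeneity analysis with site-specific estimates. Use the same model for PDA and DPDD, and align the SAP if it repeats the rule. This also settles which model the unblinded statistician fits for the stage 2 variance check (section 3.3.13).

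If the rule is kept, the minimum is one sentence stating in advance that the primary contrast is weighted by site size.

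The cost is a wording change and 1-3 degrees of freedom for two to four sites. No new data are needed. As an editorial matter, the last assessment bin, printed as 32-36, overlaps the one before it and should read 33-36.

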### 3.3 Approach

#### 3.3.1 Design Overview

The proposed investigation is a multi-site (2-4 sites), double-blind, active-controlled trial (n = 180, 90 per group) contrasting the acute and persisting effects of psilocybin to those of diphenhydramine in the context of outpatient alcoholism treatment. During the double-blind phase, participants will receive psilocybin or diphenhydramine in two monthly sessions, with dose for the second session titrated base on response in the first session. Following completion of the double-blind phase of the protocol (at week 38, 34 weeks after randomization) all participants who meet interim safety criteria will be offered an additional session in which psilocybin will be administered, and participants will be followed for an additional 16 weeks. The drug will be administered during 8 hour sessions in an outpatient setting under close medical and psychiatric monitoring. The drug administration sessions will occur in the context of a behavioral intervention consisting of an extended version of Motivational Enhancement Therapy, (Motivational Enhancement Therapy and Taking Action, META), with the addition of standardized preparation before and debriefing and follow-up after the psilocybin administration sessions. Extensive screening and baseline assessment will be completed, including thorough safety screening and assessment of participant characteristics that could potentially moderate treatment response. Within-session and short-term persisting effects will be assessed. Drinking outcomes and changes in several potential mediators of treatment effect, including motivation, self-efficacy, craving, depression, anxiety, and spiritual dimensions of the experience, will be measured for 50 weeks following initial administration of study medication (See Figure 2).

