### 3.3.2 Primary Outcome

The primary outcome for the study, used to test hypothesis 2, is percent heavy drinking days as assessed by the Time-line Follow-back [100], during the 32 weeks following the first drug administration session. Secondary drinking outcomes will include percent days abstinent, drinks per drinking day, days to first drinking day, days to first heavy drinking day, and consequences of drinking (from the Short Inventory of Problems [101]).

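### The Aim 2 Cox analyses name no baseline drinking covariate; if week 1-4 drinking predicts relapse, adding it recovers power at almost no cost

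*Combined protocol and SAP*

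**What the plan says.** Protocol section 3.3.12.3.2 sets out the primary mixed model for PHDD in detail. It includes treatment, assessment, site, two interactions and "a fixed covariate (week 1-4 PHDD"), that is, PHDD in the four weeks before the first drug session. Site is provisional: "Site and the site-by-treatment interaction will be removed from the final model if not significant at the" 0.05 level.

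The section then turns to the secondary measures on a continuous scale, which it identifies as percent days abstinent and drinks per drinking day. These "will be tested in a similar fashion and for days to first drinking day and days to first heavy drinking day"; a definition of a heavy day follows in parentheses, and the next sentence reads "Cox survival analysis will be used". No covariate or stratum is named for the Cox models.

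Three other places bear on this:
- Section 3.3.2 makes both time-to-event measures secondary: "Secondary drinking outcomes will include percent days abstinent, drinks per drinking day, days to first drinking day, days to first heavy drinking day".
- Section 3.3.5 states "The randomization will be stratified by site", and section 3.3.1 gives two to four sites.
- Section 3.3.12 says "A full description of the planned analyses for this trial can be found in the Statistical Analysis Plan (SAP"). No separate SAP text is in the combined document as available for this review.

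**The concern.** Drinking in weeks 1-4 is measured before randomisation by the Timeline Followback, and the plan already uses it for PHDD. It is a natural predictor of how soon a participant next drinks or next drinks heavily. In a Cox model, unlike a linear model, leaving out a prognostic covariate does more than add noise. It also moves the treatment HR toward 1 relative to the HR at a given level of baseline drinking, and it lowers power even under perfect randomisation.

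Two things are at stake. The relapse outcomes may miss an effect that the same data could show. And if the covariate is left open, the choice between an adjusted and an unadjusted model could be made after the data are seen.

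**Working it through.** **The plan's own figure.** There is none to reproduce: the documents give no HR, event count or power for the Cox analyses. The power statement in section 3.3.12.7 concerns PHDD only. From it I take the sample size, 180 × 0.95 = 171, and alpha 0.05 two-sided.

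**Assumed inputs.** None of these is in the documents.
- Event proportion over follow-up: 60% or 80%.
- Conditional HR: 0.62. With 1:1 allocation, the events needed for 80% power are 4 × (1.960 + 0.842)² / (ln 0.62)² = 31.4 / 0.2285 ≈ 137, and 0.80 × 171 ≈ 137. So 0.62 is the HR with about 80% power when 80% have an event and baseline drinking has no effect.
- Prognostic strength g: log-HR per SD of week 1-4 drinking, from 0 to 1.0.

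**Model.** Hazard = constant × exp(ln(0.62) × arm + g × z), with z standard normal, exponential times and administrative censoring. There were 800 trials per setting, each analysed by Cox with and without z. The Monte Carlo SE of each power figure is at most √(0.25/800) ≈ 1.8 points; both analyses use the same simulated data.

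| g | Events | HR without z | HR with z | Power without z | Power with z | Loss (points) |
|---|---|---|---|---|---|---|
| 0 | 60% | 0.615 | 0.614 | 0.669 | 0.670 | 0 |
| 0 | 80% | 0.613 | 0.611 | 0.812 | 0.811 | 0 |
| 0.25 | 60% | 0.622 | 0.616 | 0.659 | 0.672 | 1 |
| 0.25 | 80% | 0.631 | 0.617 | 0.755 | 0.786 | 3 |
| 0.5 | 60% | 0.648 | 0.619 | 0.583 | 0.657 | 7 |
| 0.5 | 80% | 0.651 | 0.615 | 0.690 | 0.809 | 12 |
| 0.75 | 60% | 0.671 | 0.617 | 0.519 | 0.672 | 15 |
| 0.75 | 80% | 0.682 | 0.612 | 0.581 | 0.804 | 22 |
| 1.0 | 60% | 0.696 | 0.616 | 0.441 | 0.677 | 24 |
| 1.0 | 80% | 0.721 | 0.616 | 0.461 | 0.787 | 33 |

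**Second set of assumptions.** 86 per arm, 32 × 7 = 224 days, control median 60 days, conditional HR 0.65, 300 trials per setting (SE up to about 3 points). For g = 0.4, 0.7 and 1.0, power was 64%, 54% and 42% without the covariate and 72%, 73% and 68% with it. The unadjusted HR was 0.68, 0.71 and 0.74. The pattern is the same.

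**Type I error.** With a true HR of 1, 70% events and a site HR of 1.5, the unadjusted test rejected in 4.3% (g = 0.5) and 5.0% (g = 1.0) of trials. With the covariate the rates were 4.0% and 4.3%.

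**Site.** Two sites, g = 0, 70% events, unstratified versus stratified power: 0.749 and 0.744 at a site HR of 1.25; 0.705 and 0.714 at 1.5; 0.662 and 0.703 at 2.0.

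**Which g is plausible?** The documents do not settle this. As an illustration only, section 3.3.6.1 requires at least 4 heavy days in 30, so entry frequency can range from 4 to 30, a ratio of 7.5. If the hazard were proportional to frequency, and frequency were spread evenly on the log scale, the SD of log-hazard would be ln(7.5)/√12 = 2.015/3.464 ≈ 0.58.

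**The case against.** The strongest reply is that the protocol is silent, which is not the same as choosing an unadjusted model. A reader might infer that the plan commits to one. The documents do not support that: the joining sentence is broken, it could be read as carrying the adjustment over, and the detail is deferred to the SAP. This stands. Even so, the adjusted approach is tied to the two named continuous measures, so someone following the text as written would most naturally fit Cox without the covariate.

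A reader might also infer that an unadjusted HR is simply wrong. It is not. The test keeps its type I error, and the estimate is a valid marginal HR. Part of the gap between the two HRs is a difference in what is being estimated, not bias.

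Progostic strength is also unknown. Weeks 1-4 are a therapy period (section 3.3.1, Figure 2), and participants must try to abstain in the week before a session (section 3.3.8.1.3). Both could weaken the link with later drinking, and at g = 0.25 the loss is only 1-3 points. This stands too. But adjustment cost nothing measurable at g = 0, so the uncertainty is not a reason to leave the covariate out.

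Two further inferences fail. Omitting a site stratum does not materially shrink the HR or cost power unless sites differ greatly. And the argument does not extend to Aim 5, where section 3.3.12.6.2 analyses the control group only and there is no treatment HR to attenuate.

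**Conclusion.** The point holds as a low-priority improvement: the protocol names no baseline drinking covariate for the two Aim 2 Cox analyses, although the data are collected and used in the primary model. If the covariate is left out, the power loss is about 0, 1-3, 7-12 or 15-22 points for g of 0, 0.25, 0.5 or 0.75. At g = 0.5 the HR reads about 0.65 where the conditional HR is 0.62.

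These sizes rest on the assumed HR, event proportions and g. They also rest on a normally distributed covariate that acts linearly on the log-hazard; PHDD is bounded and may be skewed, so the real gain could be smaller. The site stratum is worth 0-1 point up to a site HR of 1.5 and about 4 points at 2.0. Both outcomes are secondary, the trial is not powered on them, and the primary PHDD conclusion is not affected.

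**What to change.** Before unblinding, state in section 3.3.12.3.2 and in the SAP:
- The Aim 2 Cox model for time to first drink includes week 1-4 percent drinking days (100 minus percent days abstinent). The model for time to first heavy drinking day includes week 1-4 PHDD.
- The reported HR is conditional on baseline drinking. If a marginal HR is wanted, say so and say why.
- Optionally, both models are stratified by site to match the randomisation; little power gain should be expected.

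Repair the broken sentence, check it against the SAP so that the two agree, and leave Aim 5 as it is. The cost is a sentence or two and no new data. The one consequence is that the HR is read as conditional.

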#### **3.3.12.3 Aim 2 (To evaluate the effect of psilocybin treatment on drinking outcomes for 32 weeks after the first administration, relative to diphenhydramine control)**

##### **3.3.12.3.1 Outcome measures**

The primary drinking outcome for hypothesis 2 is percent heavy drinking days during weeks 5-36 (the 32 weeks following the first drug administration session) as assessed by the Time-line Follow-back [100]. Other drinking variables will serve as secondary outcomes, including percent days abstinent, drinks per

drinking day, days to first drinking day, days to first heavy drinking day, and consequences of drinking (from the Short Inventory of Problems [101]).

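### The Q statistic across drinking outcomes makes no allowance for their correlation or for opposite directions of benefit, so a non-significant Q cannot support a claim of consistent effect

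*Combined protocol and SAP*

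**What the plan says.** Section 3.3.12.3.1 sets the primary outcome: "The primary drinking outcome for hypothesis 2 is percent heavy drinking days during weeks 5-36", taken from the Time-line Follow-back. The secondary drinking outcomes are percent days abstinent (PDA), drinks per drinking day (DPDD), "days to first drinking day, days to first heavy drinking day, and consequences of drinking". That makes one primary and five secondary outcomes, all from the same randomised participants.

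Section 3.3.12.3.2 analyses percent heavy drinking days (PHDD) with a mixed model for repeated measures, and PDA and DPDD in a similar way. For the two time-to-event outcomes, "Cox survival analysis will be used". It continues: "Measures of effect size will be calculated for all planned between-group contrasts", naming Hedges d, and adds that the Q "statistic will be calculated to assess the homogeneity of effect across the primary and secondary outcome measures of drinking".

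The section gives no weights, covariance, reference distribution, significance level or decision rule for Q. It does not say how a Cox result becomes a d, or how outcomes with opposite directions of benefit are put on one footing. Section 3.3.12 refers to a Statistical Analysis Plan for the full description, but the combined document supplied contains no further text on Q.

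**The concern.** The usual Q weights each effect size by its inverse variance and refers the weighted sum of squared deviations to chi-square on k-1 degrees of freedom. That reference holds for independent effect sizes, as from separate studies. Here the k effects share the same people. When outcomes are positively correlated, their estimated effects move together, and the differences between them vary less than Q assumes. Q is then too small, and real differences between outcomes can pass unnoticed.

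Direction matters as well. Benefit raises PDA and the days to a first event, and lowers PHDD and DPDD. If the d values enter with their raw signs, a uniform benefit looks like strong heterogeneity.

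What is at stake is how the drinking results are interpreted. Q is there to assess whether the effect is homogeneous, and a non-significant result invites the conclusion that psilocybin acts consistently on all drinking measures.

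**Working it through.** **Inputs from the plan.** Section 3.3.12.7 gives 180 participants ("90 assigned to psilocybin and 90 to control"), 5% attrition, N = 171 analysed (85.5 per arm), and f² = 0.065 at power 0.8 with two-tailed alpha 0.05. Section 3.3.12.3.1 gives up to k = 6 outcomes. The number is k = 4 if the two Cox outcomes receive no d.

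**Assumptions.** The documents give no correlation between outcomes. I assume equal variances and a common correlation ρ, and show 0.3, 0.5 and 0.7. The patterns of true effects below are also assumed.

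**The plan's own figure.** The plan states no figure for Q. Its only power figure is for PHDD. With noncentrality 0.065 × 171 = 11.1, a noncentral F with 3 and 166 degrees of freedom gives power 0.798, which matches 0.8; a single-degree-of-freedom treatment test gives 0.91. The point about Q does not depend on which reading was meant. It takes only N and the scale from this section: d = 2√0.065 = 0.51.

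**Variance of one effect.** var(d) = 2/85.5 + 0.51²/(2 × 171) = 0.0234 + 0.0008 = 0.0242, so the standard error is 0.155.

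**Size of the ordinary Q, signs aligned.** With equal true effects, Q/(1-ρ) follows chi-square on k-1 degrees of freedom. The true size of the nominal 5% test is therefore P(χ² > c/(1-ρ)), where c is the usual 5% critical value. For example, with k = 6 and ρ = 0.5, c = 11.07 and the effective threshold is 11.07/0.5 = 22.14, giving 0.05%.

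| k | c | ρ = 0.3 | ρ = 0.5 | ρ = 0.7 |
|---|---|---|---|---|
| 3 | 5.99 | 1.4% | 0.25% | 0.0046% |
| 4 | 7.81 | 1.1% | 0.14% | 0.0009% |
| 6 | 11.07 | 0.74% | 0.05% | about 0.0001% |

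Simulation of Hedges d with 86 per arm and k = 6 agreed (0.8% at ρ = 0.3, 0.06% at 0.5). Unequal correlations (0.7 among five outcomes, 0.4 with the sixth) gave 0.06%.

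**Power, k = 6, ρ = 0.7.** Let S be the sum of squared deviations of the true effects from their mean. The noncentrality is λ = S/(0.0242 × 0.3). The ordinary Q rejects with probability P(χ²₅(λ) > 11.07/0.3 = 36.9). A test that uses the covariance rejects with probability P(χ²₅(λ) > 11.07).

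| True effects | S | λ | Ordinary Q | Covariance used |
|---|---|---|---|---|
| three 0.3, three 0.5 | 0.060 | 8.3 | 0.003 | 0.58 |
| three 0.2, three 0.5 | 0.135 | 18.6 | 0.09 | 0.94 |
| even spread 0 to 0.5 | 0.175 | 24.2 | 0.21 | 0.98 |
| one 0, five 0.5 | 0.208 | 28.8 | 0.36 | 0.99 |
| three 0, three 0.5 | 0.375 | 51.8 | 0.92 | 1.00 |

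The last column treats ρ as known.

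**Signs not aligned.** With benefit of 0.51 on all six outcomes, ρ = 0.7, and only PDA left in its raw direction, the ordinary Q rejects in about 97% of simulated trials, although benefit is uniform. With benefit of 0.3 it rejects in about 60%.

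**The case against.** A reader might infer that Q almost never rejects and would report a uniform effect whatever the data show. The documents do not support this. The size figures describe what happens when the true effects are equal; they do not show an inability to detect differences. At the planned N the ordinary Q still rejects in 88-98% of trials for three effects of 0 and three of 0.5 across correlations from 0 to 0.9, and in nearly all trials for three of 0 and three of 0.8. The loss is confined to modest and moderate heterogeneity.

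A reader might also infer that the plan declares the outcomes independent. It does not. The ordinary form is the natural reading of an unqualified Q paired with Hedges d, but that is an inference. A separate SAP text that specifies a covariance-based version would answer the correlation part of the point.

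The direction of the error is also not fixed. Conservatism requires aligned signs and positive correlation; with raw signs Q can err the other way.

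Finally, Q is supplementary. It has no decision rule and gates no test, and no section says that a non-significant Q will be presented as proof of consistency.

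All of this limits the point. It does not remove it: the outcomes share participants, no adjustment for that is stated, and in its ordinary form Q cannot do the job the section gives it.

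**Conclusion.** The point holds as a limited one about a supplementary analysis. With signs aligned and positive correlation, the ordinary Q has true size between 1.4% and less than 0.005% over the correlations and numbers of outcomes shown. At correlation 0.7 with six outcomes, it would miss a complete failure on one outcome, against 0.5 on the other five, about two times in three (power 0.36), where a test using the covariance would almost always find it. Large splits remain detectable. Without sign alignment, a significant Q could arise from coding alone. So a non-significant Q cannot support a consistent effect, and a significant Q is interpretable only once the coding is known.

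The sizes rest on assumed common correlations, equal variances and the inverse-variance chi-square form, none of which the documents state. The primary PHDD test is unaffected, and the priority is low.

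**What to change.** The simpler option is to drop Q and report each drinking effect with its confidence interval, all coded so that one direction means benefit.

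If a formal test is wanted, replace Q with a Wald test of equal standardised effects:

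- Code all outcomes in one direction of benefit before computing d.
- Estimate the covariance of the effects by a participant-level bootstrap: resample people, then recompute all effects in each resample.
- List the outcomes that enter. Limit them to those with a comparable effect metric, or state how the Cox results are converted.
- State that a non-significant result is not evidence of a consistent effect.

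The cost is a few lines of analysis-plan text and, for the second option, one bootstrap run. No data collection, sample size or primary analysis changes.
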